13.5.2 ANALYSIS SET FOR EFFECTIVENESS (EF)

The effectiveness analysis set will consist of all subjects who were implanted with the Gebauer™ Lenticule.

13.6 STATISTICAL ANALYSIS OF ANALYSIS SETS

The FA analysis set will serve as the main set for the safety assessments.

The EF analysis set will serve as the main set for the effectiveness assessments.

The Royal	Document No.	Version	Document Date	Author	Page: 38
Wolverhampton NHS Trust	CIP Study No. 2019OPH108	1.6	03 August 2021	[name]	Out of: 60

13.7 STATISTICAL ANALYSIS

13.7.1 GENERAL CONSIDERATIONS

Statistical analyses will be performed using appropriate statistical tools.

Baseline characteristics, together with safety analyses will be performed on all subjects from the FA analysis set. Baseline values are defined as the last valid value prior to first treatment.

The present study is mainly descriptive, nevertheless, when relevant, the required significance level of findings will be 5%. All statistical tests will be two-sided. If statistical tests are performed, nominal p-values will be presented. Where confidence limits are appropriate, a two-sided 95% confidence interval will be constructed.

For comparison of means (continuous variables), the two-sample t-test or the Wilcoxon rank sum test may be used as appropriate. For comparison of proportions (categorical variables), the Chi-squared test or Fisher's exact test may be used as appropriate.

13.7.2 DEMOGRAPHIC AND OTHER BASELINE VARIABLES

Demographic and baseline condition related characteristics will be tabulated. Continuous variables such as age and BMI will be summarized by a mean, standard deviation, minimum, median and maximum and categorical variables by a count and percentage.

13.7.3 DISPOSITION OF SUBJECTS

Treatment tolerability will be presented, the number and percent of subjects who fail to complete the study and the number and percent of subjects who fail to complete the study because of Adverse Events will be presented. Time to withdrawal may also be assessed and presented by Kaplan-Meier curves if relevant.

13.7.4 EFFECTIVENESS ANALYSIS

A repeated measures analysis (RMA) of variance model (SAS proc MIXED) may be used to assess the pain score change over time. The observed changes over time (e.g. in IOP levels or in pain score) will be modeled as a function of time with baseline results or scores entered as a covariate. Adjusted means of such variables at each time-point will be extracted from the RMA model respective 95% confidence intervals and level of significance (which assesses whether the change at that time point is significantly different from zero).

Change in corneal topography, corneal thickness, corneal clarity (the three primary endpoints for effectiveness) and all other secondary endpoints for effectiveness may be analyzed and presented in a similar manner.

The Royal	Document No.	Version	Document Date	Author	Page: 39
Wolverhampton NHS Trust	CIP Study No. 2019OPH108	1.6	03 August 2021	[name]	Out of: 60

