13.3 JUSTIFICATION OF SAMPLE SIZE

The present study is an open-label investigator initiated feasibility clinical study and will mainly be analysed with descriptive statistics. No formal sample size calculation was performed, the sample size of 15 subjects is considered sufficient to enable the estimation of the study endpoints.

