14. RISK BENEFIT ANALYSIS

14.1 BENEFITS

The purpose of this clinical investigation is to evaluate the safety of implanting the Gebauer™ Lenticule in subjects with keratoconus or post-LASIK ectasia.

The Gebauer[™] Lenticule device is indicated for use as an implantable device, which shall change the thickness and surface curvature of the patient's cornea so that a change in corneal thickness and refraction is induced.

The Gebauer[™] Lenticule has several advantages in treating keratoconus and post-LASIK ectasia as compared to alternative treatment options as described in Chapters 2.1 and 2.2. above:

• The GebauerTM Lenticule is a transparent, biocompatible corneal implant which can be

The Royal	Document No.	Version	Document Date	Author	Page: 40
Wolverhampton NHS Trust	CIP Study No. 2019OPH108	1.6	03 August 2021	[name]	Out of: 60

expected to mechanically stabilize the diseased corneal tissue without impairing the patient's vision nor his/her intraocular pressure

- The implanted collagen fibers are similar to the collagen fibers present in the natural human corneal stroma. Therefore, the implant material is expected to be fully accepted by the corneal tissue and to be integrated in its metabolism
- As the Gebauer[™] Lenticule is devoid of foreign cellular components such as cell walls, foreign proteins, lipids and foreign genetic information (DNA/RNA), the risk of immuno-logical rejection is much lower than for human cornea donor tissue transplantation.

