14.2 RISKS

Risks that may be associated with implantation of the Gebauer™ Lenticule are similar in nature to those encountered with other corneal surgeries. These risks include:

- Anterior or posterior synchie
- Cornea abrasion, opacity
- Device Detachment and further surgical manipulation
- Cornea thinning and perforation
- IOP elevation due to procedure or steroids
- Infection
- Inflammation
- Cataract induction
- Retinal detachment
- Device rejection

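### IOP and ocular pain are safety endpoints, but the only summary the protocol fixes for them is a mean-change analysis that is insensitive to large pressure rises in one to three eyes

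*Protocol*

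**What the plan says.** Protocol 5.2.2 lists changes in IOP and in ocular pain or discomfort among the secondary safety endpoints. Section 14.1 expects the implant to stabilise the cornea "without impairing the patient's vision nor his/her intraocular pressure", while 14.2 names "IOP elevation due to procedure or steroids" among the risks.

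The analysis of both variables is in 13.7.4, the effectiveness section: "The observed changes over time (e.g. in IOP levels or in pain score) will be modeled as a function of time", with baseline as covariate. Adjusted means at each time point are reported with 95% confidence intervals and a "level of significance (which assesses whether the change at that time point is significantly different from zero". For pain, the same section describes the model as optional.

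Section 13.7.1 calls the study mainly descriptive but adds that "when relevant, the required significance level of findings will be 5"%, and that "All statistical tests will be two-sided". On size, 13.3 says "the sample size of 15 subjects is considered sufficient to enable the estimation of the study endpoints"; no formal calculation was made.

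Section 13.7.5 tabulates signs of rejection and the cumulative incidence of treatment-related adverse events with a 95% interval. It also gives a full adverse event list and listings of all safety measures. It fixes no summary specific to IOP or pain. Section 15.5 states that expected events described in the plan are not counted as adverse events.

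**The concern.** For an effectiveness variable, rejecting zero change is the favourable result. For a safety variable the favourable result is absence of harm, and a test against zero in 15 eyes cannot show that.

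The mean is also a poor summary if the harm falls on a few eyes. A pressure response to surgery or steroids could do so, although the protocol does not say how many eyes to expect. A large rise in one or two eyes increases the standard error along with the mean, so the test statistic stays small.

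The other outputs may not close the gap. IOP elevation is described in the plan, so under 15.5 it could be treated as expected and left out of the adverse event rates. It would then appear only as a line in a listing, with no proportion and no interval, while the summary table shows an unremarkable mean. What is at stake is whether the report states how many eyes had a raised pressure and how large a true rate the data still allow.

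**Working it through.** **Inputs from the protocol.** n = 15 subjects with one treated eye each (sections 6 and 13.3); two-sided 5% (13.7.1); null hypothesis of zero mean change at each time point (13.7.4). The protocol gives no SD of IOP change, no relevant change, no covariance structure and no pain scale, and it states no power figure to reproduce.

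**Assumptions.** SD of IOP change 3 mmHg, varied from 2 to 5. Eyes without a spike have mean change zero.

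**Step 1: limit that does not depend on the SD.** Let k of n eyes rise by M, with M large relative to the SD. Then:

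- mean = kM/n
- variance = M² k(n−k) / [n(n−1)]
- t = mean / (SD/√n) = √[k(n−1)/(n−k)]

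With n = 15 and critical t = 2.145 on 14 degrees of freedom:

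| k | calculation | limiting t |
|---|---|---|
| 1 | √(14/14) | 1.00 |
| 2 | √(28/13) | 1.47 |
| 3 | √(42/12) | 1.87 |
| 4 | √(56/11) | 2.26 |
| 5 | √(70/10) | 2.65 |

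For one to three eyes the limit is below the critical value; from four eyes it is above.

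**Step 2: rejection rates at finite spikes.** Single-visit t-test, SD 3 mmHg, 40,000 simulated trials:

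| k | M = 0 | 5 | 10 | 20 | 40 mmHg |
|---|---|---|---|---|---|
| 1 | 0.048 | 0.050 | 0.042 | 0.014 | 0.000 |
| 2 | 0.048 | 0.075 | 0.084 | 0.040 | 0.002 |
| 3 | 0.051 | 0.126 | 0.179 | 0.168 | 0.071 |
| 4 | 0.051 | 0.197 | 0.352 | 0.509 | 0.677 |
| 5 | 0.049 | 0.304 | 0.587 | 0.877 | 0.996 |

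With SD 4, the rates for a 20 mmHg rise in one, two or three eyes are 0.025, 0.063 and 0.186.

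**Step 3: closer to the stated model.** Baseline-adjusted four-visit model, SD 3, within-subject correlation 0.5 (assumed), 20,000 simulated trials, 20 mmHg rise:

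| Variance and pattern | k = 1 | k = 2 | k = 3 |
|---|---|---|---|
| Per-visit variance, one-visit spike | 0.017 | 0.045 | 0.172 |
| Compound symmetry, rise at all visits | 0.014 | 0.042 | 0.174 |
| Compound symmetry, one-visit spike | 0.189 | 0.628 | 0.949 |

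The first two rows agree with Step 2. The third does not: visits without a spike hold the pooled variance down, so the spike is detected more often.

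**Step 4: shift shared by all eyes.** Noncentral-t power at n = 15 is 0.44 for 0.5 SD and reaches 80% at 0.78 SD. A 2 mmHg mean shift has power 0.95, 0.67, 0.44 and 0.30 for SD 2, 3, 4 and 5; a 3 mmHg shift has 1.00, 0.95, 0.77 and 0.58.

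**Step 5: what a count would show.** With no affected eye among 15, the exact two-sided 95% upper limit is 1 − 0.025^(1/15) = 0.218, or 21.8%.

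No calculation is possible for pain.

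**The case against.** The strongest reply is that the protocol never makes the p-value a verdict on safety. A reader might infer that IOP and pain safety are judged by non-significance, but the text does not support that. The study is mainly descriptive, p-values are nominal, 5% applies only where relevant, and confidence intervals stand beside the test. The primary safety endpoints are rejection and treatment-related adverse events. Section 15.4 records adverse events whatever their severity or cause, and 15.2 makes sight-threatening events serious. With 15 treated eyes, a listing shows every raised value. All of this stands, and it limits the point to the choice of summary.

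A reader might also infer that the test misses most relevant harm. The documents do not support this either: they give neither an SD nor a relevant change, and Step 4 shows that power for a shared shift may be low or high.

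It can be said that counts of affected eyes belong in a statistical analysis plan, which may add them. But the protocol does not leave the matter open. It fixes a mean-change analysis and places it under effectiveness, and that choice is what needs correcting.

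Finally, 21 mmHg is an eligibility limit, not a safety threshold. Used alone it would flag a move from 21 to 22 mmHg and not one from 10 to 20. That is fair, and it is why the largest rise per eye should be reported beside the count.

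**Conclusion.** The point holds as a mismatch between endpoint and summary. Two safety endpoints have, as their only fixed summary, a mean-change analysis under effectiveness. For IOP, a per-visit test of that mean rejects in about 1%, 4% and 17% of trials when one, two or three of 15 eyes rise by 20 mmHg. Those percentages rest on an assumed SD of 3 mmHg and no change in the other eyes; the limiting t values do not depend on the SD.

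It would be tempting to say that the test always rejects less often as spikes grow. That is not general. For two or three eyes the rate first rises and then falls; for four or more it keeps rising; and for a one-visit spike under compound symmetry it rises even for a single eye. The protocol does not fix the covariance structure, so this reversal cannot be ruled out.

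That a pressure rise may be absent from the adverse event rates is a possibility under 15.5, not a certainty. For pain, the point rests on the placement and type of summary alone.

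**What to change.** Move IOP and ocular pain from 13.7.4 to 13.7.5 and make the following their main safety summary:

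- the number and proportion of treated eyes with any post-operative IOP above 21 mmHg, with an exact 95% confidence interval. This is the entry limit from 7.2, used only as an analysis cut-off and not as a clinical rule;
- the largest IOP rise from baseline for each treated eye;
- the proportion of subjects with pain worse than baseline at each visit, with an exact 95% confidence interval.

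State the denominators, because the safety set in 13.5.1 is all enrolled subjects and 13.7.7 plans no imputation. Keep the mean change with its 95% interval as description, and add a sentence that a non-significant change is not interpreted as evidence of safety. No margin on the mean is needed.

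The cost is a wording change and one extra table from data already collected, with no added patients, visits or procedures. The downside is that wide intervals become visible.

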13.7.5 SAFETY ANALYSIS

The primary safety variables, i.e., the occurrence of signs of immunological rejection during the post implantation period, as well as the cumulative incidence (and 95% CI) of treatment-related adverse events (AEs) observed during and after implantation of the Gebauer[™] Lenticule and throughout the follow-up period, will be presented in tabular format. Related adverse events include: corneal perforation, melting, uncontrolled inflammation, severe infection

A detailed list of all adverse events will be presented. The adverse event rate will be compiled with respect to frequency, nature, severity of the event, and relationship to the study device. In addition, listings of all safety measures will be produced.

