5.2 CLINICAL ENDPOINTS

5.2.1 PRIMARY SAFETY ENDPOINTS

The following primary safety endpoints have been determined and will be systematically documented in the Case Report Form for each patient visit:

- Signs of immunological rejection during the post implantation observation period
- The frequency and severity of all treatment-related adverse events, during implantation of the Gebauer™ Lenticule and throughout the post implantation observation period.

The Royal	Document No.	Version	Document Date	Author	Page: 20
Wolverhampton NHS Trust	CIP Study No. 2019OPH108	1.6	03 August 2021	[name]	Out of: 60

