6. STUDY DESIGN AND STUDY DURATION

This investigator-initiated clinical research study is an open-label, single site clinical investigation, which follows the Good Clinical Practice guidelines as described in EN ISO 14155.

The primary aim of this study is to assess the safety and effectiveness of the Gebauer[™] Lenticules after corneal implantation in patients suffering from severe keratoconus or post-LASIK ectasia. Specific clinical endpoints, as documented in Chapter 5.2 above, have been identified in order to systematically investigate and document particularly relevant aspects of clinical safety and effectiveness of this innovative treatment option.

Subjects with severe keratoconus or post-LASIK ectasia are eligible for this study. Only subjects who have signed the informed consent form and meet all the eligibility criteria listed in Chapter 7.1 and 7.2 below will be qualified for enrollment. The study will encompass a total of 15 subjects who will complete the follow-up schedule as described in this Clinical Investigation Plan.

In summary, as listed in Chapter 8.7.5, after patients were enrolled in the study, a detailed ophthalmological examination is performed, in order to document the current status of both patient eyes (Baseline Day -30 – Day -1). On Day 0, a flap is created in the eye at the Optimax clinic, then on Day 0 (+ 30 days) patients are implanted with the GebauerTM Lenticule on 1 diseased eye. The untreated eye serves as a reference during the complete observation period.

After implantation, subjects will be followed up frequently for a period of 6 months with ophthalmic assessments at day 1-3; 28 days (+/- 7days), 3 months (+/- 14 days) and 6 months (+/- 28 days). In addition 2 weekly, telephone assessments will be conducted up to 3 months. After this period, the primary clinical investigation report will be issued.

In addition to that, two further optional patient visits are planned to investigate long-term safety and effectiveness of the Gebauer[™] Lenticules. Therefore, 1 and 2 years post implantation, patients will be invited to come back to the hospital for additional ophthalmic examinations. The results of these long-term follow-up visits will be in separate addendum reports, independently from the basic clinical investigation report.

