8.5.2 Day 0 Surgery - Flap Creation

For eligible subjects the Flap creation surgery will be scheduled according to clinical discretion of the responsible ophthalmic surgeon, and in compliance with the provisions described in this Clinical Investigation Plan. The main steps are listed here

• Under topical anesthesia, a mid-stromal pocket will be created using either a femtosecond laser dissection technique or a manual technique. In patients suffering from post-LASIK ectasia, manual techniques will be applied to re-open the pre-existing LASIK flap in the form of a pocket.

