8.5.3 Day 0 (+ 30 days) Surgery - Implantaion

For eligible subjects the Implantation of the Gebauer[™] Lenticule surgery will be scheduled according to clinical discretion of the responsible ophthalmic surgeon up to 30 days after the flap creation, and in compliance with the provisions described in this Clinical Investigation Plan. The main steps are listed here

- Under topical anesthesia, the corneal vertex will be marked with gentian violet using the first Purkinje image as a reference while asking the patient to fixate on the microscope light.
- The Gebauer™ Lenticule implant is then gently inserted and fully expanded with no wrinkles into the pocket through the pocket opening.
- The implant is then centered with the corneal vertex.
- Immediately post implantation, essential surgical data will be recorded including procedural details (start and end time), orientation, dimensions and closure method of pocket, use of bandage contact lens, device ease of use, procedure complications and medications prescribed.

The subject will be discharged after the procedure or will be hospitalized for one day according to physician discretion.

The Royal	Document No.	Version Document Date		Author	Page: 26
Wolverhampton NHS Trust	CIP Study No. 2019OPH108	1.6	03 August 2021	[name]	Out of: 60

Post- operatively, antibiotic eye drops will be prescribed for 2 weeks, and steroid eye drops (e.g. PredForte; Allergan) will be prescribed 2 hourly for 2 weeks, along with optional lubricating drops.

Safety Monitoring will be performed (recording of adverse events and medications)

The Royal	Document No.	Version	Document Date	Author	Page: 27
Wolverhampton NHS Trust	CIP Study No. 2019OPH108	1.6	03 August 2021	[name]	Out of: 60

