15. SAFETY PARAMETERS

Safety assessments include sings of immunological rejection during the post implantation observation period and adverse events/serious adverse events. These variables are classified as primary safety endpoints. Further to this, changes in IOP, corneal /lenticule transparency, inflammation, changes to the corneal epithelium, conjunctiva, iris/pupil or the intraocular lens as well as changes to ocular pain/discomfort have been classified as secondary safety variables.

The reporting time period for safety variables starts with the baseline ocular examination and ends with the last follow-up results obtained after 6 months, respectively, after 2 years post implantation.

The Royal	Document No.	Version	Document Date	Author	Page: 41
Wolverhampton NHS Trust	CIP Study No. 2019OPH108	1.6	03 August 2021	[name]	Out of: 60

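### The start of the primary safety window is contradictory, and as defined and analysed it misses the first of the two operations

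*Protocol*

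**What the plan says.** **Two operations.** Section 6 of the protocol states: "On Day 0, a flap is created in the eye at the Optimax clinic". Section 8.5.2 describes that step: "a mid-stromal pocket will be created using either a femtosecond laser dissection technique or a manual technique", or, in post-LASIK ectasia, manual re-opening of the old flap. Section 8.5.3 schedules implantation as a further surgery, "up to 30 days after the flap creation". Section 8.5 and the schedule in 8.5.9 treat the two as separate visits. The synopsis includes pocket formation in its description of the study treatment.

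**Primary safety endpoint.** Section 5.2.1 defines it, beside signs of rejection, as "The frequency and severity of all treatment-related adverse events, during implantation" and through the period after implantation. The synopsis has the same start. Section 13.7.5 analyses it as the "cumulative incidence (and 95% CI) of treatment-related adverse events (AEs) observed during and after implantation" and through follow-up. None of the three mentions pocket or flap creation.

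**Section 15.** This section classes adverse and serious adverse events as primary safety endpoints and says that the reporting period for safety variables "starts with the baseline ocular examination".

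**Collection and analysis set.** The schedule in 8.5.9 marks adverse event documentation at every visit, including flap creation. Section 8.5.6 requires an adverse event form when the procedure fails or surgery is abandoned. Section 15.4 records relationship to device and to procedure separately. Section 13.7.5 promises a list of all adverse events, but its summary of the event rate names relationship to the device only. The safety set (13.5.1, 13.6) is all enrolled subjects.

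**The concern.** Cutting or re-opening the stroma of a severely ectatic cornea is an intervention with its own risks. Section 13.7.5 itself gives corneal perforation and severe infection as examples of related events, and either could plausibly arise at this stage. A primary rate whose clock starts at the second operation does not describe the safety of the whole treatment, and it can only err downwards.

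The contradiction adds a second problem. Read through 5.2.1 and 13.7.5, an event between the two operations is not a primary event; read through section 15, it is. The same data would then support two primary safety rates. The study is open label, so the choice between them could be made after the events are known.

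**Working it through.** The protocol gives no event rate, power statement or sample size formula for this endpoint, so there is no figure to reproduce. The check is a comparison of passages followed by arithmetic for scale.

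**1. Start of the window, place by place**

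| Place in the protocol | Start for adverse events | Pocket stage inside? |
|---|---|---|
| Synopsis, primary safety endpoint | implantation | no |
| 5.2.1 | implantation | no |
| 13.7.5, cumulative incidence and CI | implantation | no |
| 13.7.5, list of all adverse events | no start given | yes |
| 15, primary safety variables | baseline examination | yes |
| 8.5.9, documentation of events | baseline visit | yes |

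Implantation cannot be read as shorthand for both operations, because sections 6, 8.5, 8.5.2, 8.5.3 and 8.5.9 all separate them.

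**2. Which events are missed.** Section 13.7.5 counts events observed during and after implantation, not only those with onset then. An event that begins at the pocket stage and is still present at implantation can therefore count. Two kinds cannot: a related event that resolves before implantation, and one that stops implantation from taking place. In both cases the patient remains in the denominator, because the safety set is everyone enrolled.

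**3. Size per patient.** Inputs: n = 15 (13.3); section 10 allows replacements up to 20%, that is 0.20 × 15 = 3, so at most 18 enrolled. One patient is 1/15 = 6.7 percentage points, or 1/18 = 5.6 points.

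The protocol asks for a two-sided 95% interval without naming a method. I assume the exact (Clopper-Pearson) interval: lower limit = Beta quantile 0.025 with parameters (x, n − x + 1); upper limit = Beta quantile 0.975 with parameters (x + 1, n − x). For x = 0 the upper limit is 1 − 0.025^(1/n); with n = 15 that is 0.218.

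Suppose, as an assumption, that the only related events are of the missed kind:

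| Patients with such an event | Window from implantation | Window from pocket creation |
|---|---|---|
| 1 of 15 | 0% (0 to 21.8%) | 6.7% (0.2 to 31.9%) |
| 2 of 15 | 0% (0 to 21.8%) | 13.3% (1.7 to 40.5%) |
| 3 of 15 | 0% (0 to 21.8%) | 20.0% (4.3 to 48.1%) |
| 1 of 18 | 0% (0 to 18.5%) | 5.6% (0.1 to 27.3%) |

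**4. Chance that it matters.** The protocol gives no pocket-stage risk, so a range is assumed. If p is the risk per patient of a related event of the missed kind, the chance of at least one in 15 patients is 1 − (1 − p)^15:

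- p = 2%: 26%
- p = 5%: 54%
- p = 10%: 79%
- p = 20%: 96%

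**The case against.** The best defence is that the protocol does capture pocket-stage harm. Events are documented at the flap visit, an abandoned operation generates an adverse event form, every event is listed, relatedness is judged against study procedures as well as the device (15.9), and section 15 already treats these events as primary. In a small, mainly descriptive study with no threshold or stopping rule tied to this rate, a perforation at the pocket stage would be visible to any reader of the listing.

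Most of this stands, and it limits the point in three ways.

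- A reader might infer that harm from making the pocket is left out of the study's safety data. The documents do not support that. It can be missing only from the primary cumulative incidence and its interval.
- A reader might infer that a patient harmed before implantation, and so never implanted, contributes no event at all. That is also too strong: sections 8.5.6 and 13.7.5 put the event on a form and in the list. It misses the primary numerator.
- It is tempting to size the omission by time at risk: 30 / (30 + 182) = 14%, taking 182 days for six months. That uses the longest permitted gap. Section 8.5.3 sets 30 days as an upper limit, so the gap may be close to zero, and calendar days are a poor measure of surgical risk.

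What the defence does not do is repair the primary rate. A listing is not an incidence with a confidence interval, and section 15 covers the pocket stage only by contradicting 5.2.1 and 13.7.5. Nor is this a detail left to the analysis plan, because the protocol fixes the window itself, in two ways.

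**Conclusion.** The point holds as a contradiction in the start of the primary safety window. In the synopsis, 5.2.1 and 13.7.5 the window begins after the first operation; in section 15 it begins at baseline. Under the former, a related event that resolves before implantation or prevents it is outside the primary numerator, while the patient stays in the denominator. The resulting bias is downwards.

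Each affected patient is worth 6.7 percentage points with 15 enrolled, or 5.6 with 18. Whether there will be any depends on the interval actually used between the operations and on a pocket-stage risk the protocol does not state. The event counts and risks used above are assumptions, as is the exact interval. No figure in the protocol is wrong.

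This should be fixed, preferably before any events are seen. Because the events are collected and listed in any case, it does not undermine the study as a whole.

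**What to change.** 1. In the synopsis, 5.2.1, 13.7.5 and section 15, give the treatment-related adverse event endpoint one start: the start of pocket or flap creation. Section 15 can still collect safety data from baseline if it separates collection from the endpoint.
2. Keep the existing end of follow-up: 6 months for the main report, with the long-term visits in the addenda.
3. Leave signs of immunological rejection as a post-implantation endpoint.
4. In 13.7.5, tabulate events by stage (pocket, implantation, follow-up) and by relationship to procedure as well as to device.
5. State that a patient with a pocket but no implant counts in the numerator if a related event occurs.

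Separately, the schedule table in 8.5.9 gives implantation as 0 ± 30 d, whereas the synopsis, section 6 and 8.5.3 give Day 0 + 30 days. These passages must be reconciled.

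The cost is wording only, since the events and both relationships are already recorded. The stated rate may come out slightly less favourable.
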